8.2. STUDY DAY

Study day will be calculated with respect to the date of the first dose of open label study drug. For assessments conducted on or after the date of the first dose of open label study drug, study day will be calculated as:

(Assessment date – date of first dose of open label study drug) + 1

For assessments conducted before the date (and time) of the first dose of open label study drug, study day will be calculated as:

(Assessment date – date of first dose of study drug).

8.3. DURATION OF TREATMENT AND COMPLIANCE

Treatment duration is defined as the duration of time from the date of the first dose of study drug of open label lonapegsomatropin in the extension period to the date of the last dose of in the extension period as follows:

Duration of treatment (day) = Last dose date of treatment – first dose date of treatment + 7

Treatment compliance = 100 * (Number of actual doses taken/total number of planned doses), where the total number of planned doses= (Duration of treatment/7).

8.4. AGE

Unless otherwise specified, the age will be the integer value of the derived value which will be based on the informed consent date: Age = (Informed Consent Date – Birth Date)/365.25. When date of birth is missing, the age recorded on CRF at the screening visit will be used.

If birth date is missing and age recorded on CRF is also missing, the birth date will be imputed (see Section 10.3) before calculating the age.

For a specific measurement, Age (years) = (Date of measurement – Birth Date)/365.25 and Age (months) = (Date of measurement – Birth Date)/365.25*12.

8.5. BASELINE MEASUREMENTS

Unless otherwise specified, baseline used in this study will be the extension period baseline, defined as the TCH-306 Visit 7 assessments or the last assessment taken on or prior to the first dose of study drug in TCH-306EXT, whichever occurs later considering date and time.

For the subjects that switched from commercially available daily somatropin treatment (Japan only), baseline value is defined as the last measurement on or before the first administration date (if time is not available) of study drug in the extension period.

8.6. TREATMENT GROUP

Subjects in the extension period will be classified into one of the following treatment groups based on the treatment group the subject was randomized in the main treatment period of TCH-306 (foresiGHt):

- Lonapegsomatropin/Lonapegsomatropin
- Daily Somatropin/Lonapegsomatropin
- Placebo/Lonapegsomatropin

Subjects that switched from commercially available daily somatropin treatment (Japan only) will be classified as:

- Commercial Switch

9. ANALYSIS POPULATIONS

Number and percent of patient meeting the definition of each analysis population will be summarized by treatment group.

9.1. SAFETY ANALYSIS POPULATION

All subjects who are exposed to any amount of the lonapegsomatropin in TCH-306EXT. All efficacy analysis will be conducted using this population

A large black rectangular redaction box covering several lines of text.

10. DATA SCREENING AND ACCEPTANCE

10.1. GENERAL PRINCIPLES

Data will be reviewed periodically. Any discrepant data will be reported to the clinical data manager promptly for query and resolution. The observed data will be reported as is in listings. Imputed data will be used for summary analysis.

10.2. HANDLING OF MISSING AND INCOMPLETE DATA

Missing clinical outcome data can occur for multiple reasons, including missed subject visits and scales or measures with missing item scores. Missing and incomplete data will be identified through the data review plan for this study. Missing and incomplete data will be identified for investigation, and possible resolution by Data Management prior to the study database lock or snapshot.

Unless specified otherwise, only the observed data (not imputed data) will be presented in listings.

10.3. MISSING BIRTH DATES

To impute missing birth date, the following rules will be applied:

- If day is missing, impute 15.
- If month is missing, impute June.
- If year is missing, then no imputation will be done; the date will be missing.

If the imputed date is later than any study visit date/observed adverse event start date/ observed concomitant medication start date or any event start date, then earliest available visit date/adverse event start date/ concomitant medication start date or any event start date will be used without changing observed information.

10.4. MISSING MEDICAL HISTORY RELATED DATES

- If only day is missing, impute 1.
- If month is missing, impute January 1st.
- If year is missing, then no imputation will be done; the date will be missing.

If the imputed date is earlier than the birth date, then the birth date will be used.

10.5. MISSING DATES IN ADVERSE EVENTS

For determination of treatment-emergent adverse event (TEAE), if the start date and time of an AE are partially or completely missing, the AE will be assumed to be treatment-emergent if it cannot be definitively shown that the AE did not occur or worsen on or after the first dose in the study (worst case approach).

The following rules will be used for TEAE determination where the AE has a missing start date.

If the start time of an AE is missing, but the start date is complete, an AE will only be excluded from treatment-emergent AEs if the start day is before day of first treatment or the start day is after end of study day.

If the start time and day are missing but the start month is complete, an AE will only be excluded from treatment emergent AEs if the start month is before month of first treatment or the start month is after end month of end of study month or if the stop date/time is before the start of first treatment.

If the start day and months are missing but the start year is complete, an AE will only be excluded from treatment-emergent AEs if the start year is before year of first treatment or if the start year is after end of study year or if the stop date/time is before the start of first treatment.

If the start date is completely missing, an AE will not be excluded from treatment emergent AEs unless the stop date/time is before the start of first treatment.

10.6. MISSING DATES IN PRIOR AND CONCOMITANT MEDICATION

If the start/stop dates of a medication are partially or completely missing, then the medication will be assumed the medication was administered concurrently during the treatment period, unless there is evidence to show otherwise.

The on-treatment period is defined as the time from the first dose to 7 days after the last dose of lonapegsomatropin.

10.7. MISSING CAUSAL RELATIONSHIP TO THE STUDY DRUG FOR ADVERSE EVENTS

If the causal relationship to the study drug is missing for an AE that started on or after the date of the study drug administration, a causality of “related” will be assigned. The imputed values for causal relationship to study drug will be used for the incidence summary; the values will be shown as missing in the data listings.

10.8. VISIT TIME WINDOWS

All post-baseline visits will be mapped to the post-baseline scheduled visit with the closest target study day for each scheduled assessment with exception of DXA data, [REDACTED] parameters.

If the unscheduled visit is in the middle of two scheduled visits, it will be mapped to the later one. After mapping, if there is more than one visit in the same window, the visit closer to the target assessment day will be used. If more than one visit has an equal distance to the target day, then the later one will be used; if more than one visit occurs on the same day, the time or the sequence number will be used to select the later record. For listings, all data points (as observed) will be included.

Table 2: Analysis Window (All Parameters Except DXA, [REDACTED] Parameters)

[figure not shown]
PERIOD	VISIT	Week	Target Study Day	Study Day Window
Extension	Visit 8	Date of first open label study drug	X1	<=1
	Visit 9	(EXTENSION) Week 4	X1+ 28	(X ₁ +1) - (X ₁ +42)
	Visit 10	(EXTENSION) Week 8	X1+ 56	(X ₁ +43) - (X ₁ +70)
	Visit 11	(EXTENSION) Week 12	X1+ 84	(X ₁ +71) - (X ₁ +101)
	Visit 12	(EXTENSION) Week 17	X1+ 119	(X ₁ +102) - (X ₁ +157)
	Visit 13	(EXTENSION) Week 28	X1 +196	(X ₁ +158) - (X ₁ +231)
	Visit 14	(EXTENSION) Week 38	X1 +266	(X ₁ +232) - (X ₁ +315)
	Visit 15	(EXTENSION) Week 52	X1 + 364	(X ₁ +316) - (X ₁ +413)
Safety follow-up/End of Study		Safety follow-up	Date of last dose + 28 days	(Date of last dose date + 14 days) - (Date of last dose + 49 days)

Study day in the extension period is calculated with respect to the date of the first dose of study drug. X₁= First dose date of Open Label extension in study day in reference to the first dose day from the main period.

For the analysis of efficacy endpoints and [REDACTED] assessed by DXA, following study day window will be used:

- (EXTENSION) Week 12: analysis will be performed based on the assessments performed at the scheduled visit.
- (EXTENSION) Week 52: analysis will be performed based on the assessments performed at the scheduled visit.

If there are more than one DXA assessment in the same visit, the visit closer to the target assessment day will be used. If more than one DXA assessment with an equal distance to the target day, then the later one will be used in the analysis.

10.9. TESTING/VALIDATION PLAN

Data will be periodically reviewed by the cross functional team and issues will be addressed by Clinical Data Management.

10.10. SOFTWARE

SAS® software version 9.4 or higher will be used to perform statistical analyses unless otherwise specified.

11. STATISTICAL METHODS OF ANALYSES

11.1. GENERAL PRINCIPLES

In general, summaries will be performed descriptively by treatment group. Continuous, quantitative (absolute values at each time point and change from baseline if applicable) variable summaries will include the number of subjects (N) with non-missing values, mean, standard deviation (SD), standard error (SE) of the mean, median, minimum, and maximum values.

Categorical, qualitative variable summaries will include the frequency and percentage of subjects in the particular category. In general, the denominator for the percentage calculation will be based upon the total number of subjects in the study population for the cohorts.

All statistical tests will be two-sided and tested at statistical significant level of 0.05. P-values will be rounded and displayed in three decimals. If a p-value is less than 0.0001, it will be shown in tables as <0.0001. Confidence intervals will be 2-sided 95% confidence intervals, unless stated otherwise.

Unless otherwise specified, all summaries including by-visit summaries will be analyzed for the extension period (52 weeks of treatment) and for the commercial switch population, all analyses will be repeated and analyzed separately.

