11.11. SAFETY ANALYSIS

Unless otherwise specified, safety analyses will be performed using the Safety Analysis population for the extension period. The safety parameters will include adverse events (AEs), clinical laboratory, vital sign, electrocardiographic (ECG) parameters, MRI, fundoscopy, immunogenicity, and other safety parameters if collected. For safety endpoints, all analyses will be based on the observed data (i.e., with no imputation of missing data), unless otherwise stated. These summaries will be presented by treatment group in the extension period.

Adverse events will be coded by system organ class (SOC) and preferred term (PT) using the Medical Dictionary for Regulatory Activities (MedDRA) Version 26.0.

An extension period AE (classified by preferred term) will be considered as treatment emergent adverse event (TEAE) if it occurred on or after the first dose of open-label lonapegsomatropin and was not present prior to the first dose of open-label lonapegsomatropin, or it was present at the first dose of open-label lonapegsomatropin but increased in severity during the study through 14 days after the last dose of treatment on the extension period.

A TEAE that started on or after the first dose date of open-label lonapegsomatropin will be counted as extension period TEAE.

- Summary of TEAEs by treatment
- TEAEs by treatment, SOC and PT (sorted by descending frequency by SOC and PT)
- TEAEs by treatment, SOC and PT Reported by > 5% of subjects in any treatment group
- Related TEAE by treatment, SOC and PT
- Serious TEAEs by treatment, SOC and PT (sorted by descending frequency by SOC and PT)
- Serious Related TEAEs by treatment, SOC and PT (sorted by descending frequency by SOC and PT)
- AEs leading to death by treatment, SOC and PT (sorted by descending frequency by SOC and PT)
- TEAEs leading to discontinuation of study by treatment, SOC and PT (sorted by descending frequency by SOC and PT)
- TEAEs leading to discontinuation of treatment by treatment, SOC and PT (sorted by descending frequency by SOC and PT)
- TEAEs by treatment and PT (sorted by descending frequency of PT)
- Related TEAEs by treatment and PT (sorted by descending frequency of PT)
- Serious TEAEs by treatment and PT (sorted by descending frequency of PT)
- Deaths by treatment

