11.11.2. Other Adverse Events to Monitor

11.11.2.1. Clinical Laboratory Parameters

Descriptive summaries of actual (absolute) values and changes from baseline values if applicable will be presented for the following by treatment and visit:

- Chemistry: sodium, potassium, calcium, chloride, total bilirubin, alkaline phosphatase, lactate dehydrogenase (LDH), aspartate aminotransferase (AST), alanine aminotransferase (ALT), gamma glutamyl transferase (GGT), albumin, total proteins, creatinine (also eGFR calculation per MDRD equation), urea-nitrogen, uric acid, ferritin, and transferrin
- Hematology: hemoglobin, erythrocyte count, hematocrit, mean corpuscular hemoglobin (MCH), mean corpuscular volume (MCV), mean corpuscular hemoglobin concentration (MCHC), leukocytes, differential blood count of leukocytes, platelet count
- Glucose Metabolism: fasting insulin, fasting glucose, HbA1c
- Lipid Metabolism (fasting): total cholesterol, triglycerides, HDL, LDL, Lp(a) lipoprotein, free fatty acids, VLDL
- Thyroid and adrenal status: TSH, fT4, fT3, morning (06:00-10:00AM) cortisol
- Testosterone (males only)

Laboratory values will be displayed in the data listings and those that are outside the normal range will be flagged, along with corresponding normal ranges

Data listings of laboratory will also be provided, displaying details of each laboratory test for central and local laboratories separately.

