11.11.2.2. Antibodies

The appropriateness of the approach taken to analyze and report anti-drug antibody data should be evaluated on a case-by-case basis ([FDA Guidance for Industry 2016](#)), following recent regulatory guidance and a white paper ([Shankar G 2014](#)). Statistical analysis of antibodies against drug (ADA) will include (but not be limited to) the following tabulated summaries of antibody frequencies and percentages:

- Incidence of pre-existing anti-hGH binding antibodies (positive Baseline)
- Incidence of treatment induced anti-hGH binding antibodies by positive types (treatment emergent positive and treatment boosted positive) and overall
- Incidence of treatment induced, transient anti-hGH binding antibodies by positive types (treatment emergent positive and treatment boosted positive) and overall
- Incidence of treatment induced anti-hGH neutralizing antibodies by positive types and overall

In addition, treatment induced anti-TransCon hGH and anti-PEG binding antibodies will also be summarized by visit and positive types and overall.

Treatment induced ADA will include two positive types:

- Treatment emergent positive: if baseline (pre-treatment sample) is negative for ADA and post-treatment sample is positive for ADA
- Treatment boosted positive: if baseline (pre-treatment sample) is positive and post-treatment sample has a titer which is at least 4-fold higher than the pre-treatment sample.

The baseline antibody status is the status before the first dose of lonapegsomatropin.

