11.11.2.3. Vital Signs

Descriptive statistics for vital signs (systolic and diastolic blood pressures, pulse rate, BMI and weight) and changes from baseline values at each visit and at the end of study will be presented by treatment group.

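### The SAP's default percentage denominator, applied as written, counts participants with no sample as not positive in the by-visit antibody table and keeps unclassifiable participants in overall antibody incidence.

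*SAP*

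**What the plan says.** SAP 11.1 (General Principles) gives two different rules. Continuous summaries report "the number of subjects (N) with non-missing values". For categorical summaries, as a general default, "the denominator for the percentage calculation will be based upon the total number of subjects in the study population for the cohorts".

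SAP 11.11.2.2 (Antibodies) plans antibody frequencies and percentages. After the anti-hGH items it adds that "treatment induced anti-TransCon hGH and anti-PEG binding antibodies will also be summarized by visit and positive types and overall". It names no denominator. It defines two kinds of treatment-induced positive, and both compare a post-treatment sample with a pre-treatment one: negative turning positive, or positive with a titre at least 4-fold higher.

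SAP 11.11 (Safety Analysis) adds that for safety endpoints "all analyses will be based on the observed data (i.e., with no imputation of missing data), unless otherwise stated". SAP 10.1 pulls the other way for data in general: "Imputed data will be used for summary analysis".

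Immunogenicity is listed among the endpoints of the primary safety objective in protocol Section 3. Under the protocol's Schedule of Activities, antibody samples are taken at screening, at Weeks 4, 12, 17, 28, 38 and 52, and at the last follow-up visit.

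**The concern.** A whole-population denominator is the usual choice for adverse events, where every exposed participant is at risk and under observation for the event. A laboratory status at a given visit is different, because it is known only for those sampled. Dividing by everyone prints a percentage that implies a negative result for each participant without one.

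The trial tests no formal hypotheses (protocol 9.1), so the displayed percentages are themselves the immunogenicity result. The error can only lower them, which is the favourable direction for a safety endpoint. If more samples are missing at later visits, positivity would drift down down the table for that reason alone. If treatment groups differ in missing samples, a difference between groups could appear with no difference in antibodies.

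**Working it through.** **Which outputs the default reaches.** From the visible text of SAP 11.11 and its subsections:

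| Output | Type | Affected? |
|---|---|---|
| Anti-TransCon hGH and anti-PEG antibodies | categorical, by visit | yes |
| Overall treatment-induced antibody incidence | categorical, whole period | yes, through unclassifiable participants |
| Laboratory values: "Descriptive summaries of actual (absolute) values and changes from baseline values if applicable will be presented" | continuous | no, non-missing N applies |
| Vital signs: "changes from baseline values at each visit and at the end of study will be presented by treatment group" | continuous | no |
| ECG parameters | continuous | no |
| Fundoscopy and MRI | listings | no |
| Adverse events, injection site reactions | counts over the period | no, exposed population is the usual denominator |

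**Inputs.** The plan has no figure to reproduce: it gives no dropout rate, missing-sample rate or antibody rate. SAP 4 gives 220 participants from TCH-306 and 13 commercial-switch participants. The values of d and p below are assumptions.

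**Formula.** Let N be the population, d the fraction with no sample at the visit, and p the positivity among those sampled. Positives = p × N(1−d), so:

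- displayed percentage = p × N(1−d) / N = p(1−d)
- absolute shortfall = p × d
- relative shortfall = d

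**Range.**

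| p among sampled | d = 5% | d = 10% | d = 20% |
|---|---|---|---|
| 2% | 1.9% | 1.8% | 1.6% |
| 10% | 9.5% | 9.0% | 8.0% |
| 20% | 19% | 18% | 16% |

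The absolute shortfall runs from 2% × 5% = 0.1 to 20% × 20% = 4.0 percentage points.

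**Worked counts.**

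- N = 220, 10% missing (198 sampled), 20 positive: 20/220 = 9.1% displayed, 20/198 = 10.1% among those sampled.
- N = 220, 20% missing (176 sampled), 20 positive: 9.1% displayed, 20/176 = 11.4% among those sampled.
- Commercial-switch group, N = 13, 3 missing, 1 positive: 1/13 = 7.7% displayed, 1/10 = 10.0% among those sampled.

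**Between groups.** With 10% positivity in both, but 5% missing in one group and 20% in the other, the table shows 9.5% against 8.0%. The denominator alone creates that difference.

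**Overall incidence.** The same formula applies, with the unclassifiable fraction u in place of d. Participants with no post-baseline sample at all are a subset of those missing at any one visit. TCH-306 Visit 7 assessments are required for entry (protocol 5.1), so for participants from TCH-306 missing baselines should be few. For them u should therefore usually be smaller than d at a late visit.

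**The case against.** The strongest reply is that the 11.1 rule is hedged as a general one and that 11.11, the section specific to safety, calls for observed data without imputation. Read together, these could point to participants with a result. That reading is possible, but it is not what the text fixes. The 11.11 sentence bars filling in values and does not set a denominator. A programmer can impute nothing, divide by the whole group, and comply with both sections.

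A second reply is that 11.11.2.2 leaves the antibody approach to case-by-case evaluation under external guidance, and that redacted text may hold further definitions. Neither can be ruled out. The point is therefore limited to the visible text, where the default is the only denominator given.

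A third reply is that there are mitigations. Protocol 8.7 asks for an antibody sample at the final visit from those who discontinue. SAP 10.8 maps visits to windows. Counts are shown beside percentages, and the data are listed. These reduce the number of missing samples and let a careful reader check, but they do not correct the printed percentage.

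Two stronger readings are tempting. A reader might infer that the SAP deliberately counts missing participants as negative. It does not say so; this follows only if the default is applied literally. A reader might also infer that by-visit safety results in general, or adverse event incidence, are understated. The table of outputs above does not support that: only the anti-TransCon hGH and anti-PEG summaries are visibly both categorical and by visit.

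**Conclusion.** The point holds in this limited form. For the by-visit antibody table, the only denominator the SAP states gives p(1−d) rather than p. For overall treatment-induced incidence it retains participants whose status cannot be determined. The direction is certain whenever samples are missing. The size is not known, because it rests wholly on assumed missing rates: a relative understatement of 5% to 20% for d of 5% to 20%, and none if every sample is obtained.

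The severity is minor to moderate. The trial is descriptive and no visible decision depends on a by-visit antibody percentage. Still, the figures belong to a primary safety endpoint, and any error makes them look better.

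**What to change.** Add to SAP 11.1 or 11.11.2.2, before database lock:

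- By-visit antibody percentages, and any other by-visit categorical summary, use as denominator the participants with a non-missing result at that visit. Show that n in each row.
- Treatment-induced antibody incidence uses participants with a baseline and at least one post-baseline sample.
- Adverse event tables keep the full Safety Analysis Population.

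It would help to say in the same place how the observed-data rule in 11.11 relates to 11.1 and to the imputation sentence in 10.1.

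The cost is a sentence or two in the SAP and one extra n per table row. Reported rates may be slightly less favourable. The change does not remove informative dropout: protocol 7.1 stops treatment for confirmed neutralizing antibodies, so some positive participants may lack later samples. Showing the n at each visit makes that loss visible but does not adjust for it.
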